5.6 Treatment Regimen and Dosing

The treatment groups are shown in Table 7. Patients randomized to 1 of the Bimatoprost SR dose groups will receive an intracameral administration of Bimatoprost SR in the study eye on Day 1, Week 16, and Week 32, in addition to using topical vehicle eye drops (1 drop BID). They will receive timolol eye drops (1 drop BID) plus Sham administration in the fellow eye. Patients randomized to the Control group will receive a Sham administration in both eyes on Day 1, Week 16, and Week 32, in addition to timolol eye drops (1 drop BID) in both eyes.

After the Administration Day 1 visit (Bimatoprost SR or Sham administration procedure), the patients should start administration of the study-provided eye drops in both eyes, starting with the evening dose. Patients should continue administering study-provided eye drops in the morning (at 08:00 ± 1 hour) and in the evening (20:00 ± 1 hour), approximately 12 hours apart. Patients will be instructed not to administer the study-provided eye drops on the morning of study visits (except administration visits), and to bring their study medications to their visit for instillation immediately after the Hour 0 IOP measurements. If the patient arrives having taken the morning dose of study-provided eye drops, the site should attempt to reschedule within the visit window. Exception is made for the Day 2 study visit after any injection. As this visit is primarily for safety purposes, patients should undergo the visit regardless of whether they did or did not use the study medication that morning. Site personnel and patients will be reminded to take appropriate caution during administration of study medications during the visit to ensure maintenance of masking.

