5.10 Retreatment

Administration of Bimatoprost SR will occur at fixed intervals of 16 weeks, up to a total of 3 administrations. Patients will be readministered the Bimatoprost SR dose strength to which they were randomized unless in the investigator's opinion it would not be in the best interest of the patient to readminister Bimatoprost SR based on previous adverse events or safety concerns. Patients who have been treated with nonstudy IOP-lowering medication in only one eye will still attend administration visits; if the treated eye is the Bimatoprost SR study eye, the patient will receive a Sham administration in that eye. Control group study eyes and fellow eyes that have been treated with nonstudy IOP-lowering medications will continue to receive Sham administrations. Patients who have been treated with nonstudy IOP-lowering medication in both eyes will not attend the Administration Day visits, nor will they attend the Day 2, Days 4 and 8 (phone call), or the 2-week visits (ie, Weeks 2, 18, and 34) following an administration.

6. Response Measures and Summary of Data Collection Methods

Detailed information on equipment and methodology to be used is provided in the Protocol Procedure Manual.

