11.0 SAFETY ANALYSES

The safety analysis will be performed using the safety population. The safety parameters will include the following nonocular safety parameters: nonocular AEs, clinical laboratory values, vital signs, and pregnancy; [REDACTED]

[REDACTED] Unless otherwise stated, the last nonmissing safety assessment before the first dose of study treatment will be used as the baseline for all analyses of that safety parameter. Continuous variables will be summarized by number of patients and mean, SD, median, the 1st quartile and the 3rd quartile, minimum, and maximum values. Categorical variables will be summarized by number and percentage of patients.

[REDACTED]

For all safety by-cycle summary analyses, in order to compare cycles of similar duration, the data included in each cycle will be,

- Cycle 1 (16 weeks): data from the 1st injection to the 2nd injection date -1 or upper bound of week 15 visit window (section 16.1) if a patient didn't receive the 2nd injection;
- Cycle 2 (16 weeks): data from the 2nd injection to the 3rd injection date -1 or upper bound of week 31 visit window (section 16.1) if a patient didn't receive the 3rd injection;
- Cycle 3 (20 weeks): data from the 3rd injection to upper bound of week 52 visit window (section 16.1);
- Extended safety follow up: data after week 52 for patients with 3 injections and extended follow up.

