11.1 ADVERSE EVENTS

Adverse events will be coded by SOC and preferred term using the Medical Dictionary for Regulatory Activities.

For a given AE and patient, if more than 1 severity grade is reported, the worst severity grade (the greater of the onset and maximum severity recorded on the electronic case report from [eCRF]), will be used for analysis.

Adverse events will be classified into ocular AEs and nonocular AEs. An ocular AE will be determined as indicated on the AE form of eCRF, and thus are not limited to AEs with primary SOC of eyes. The treatment-related ocular AEs will be further broken down by either related to injection procedure or related to study drug as indicated on eCRF. Ocular AEs will be tabulated by treatment group for the study eye and pooled for the fellow eye, and nonocular AEs will be summarized by treatment group for patient. Analysis by cycle of treatment will also be performed.

Treatment-Emergent Adverse Events

An AE will be considered a treatment-emergent adverse event (TEAE) for the study treatment period if the AE meets 1 of the following criteria:

- The onset date is on or after the first study treatment date.
- The onset date is before the first study treatment date and either:
 - The severity of the event worsened on or after the first treatment date.
 - The event became serious on or after the first study treatment date.

An AE will be considered as a TEAE for a treatment cycle if the AE meets 1 of the following criteria:

- The onset date is on or after the treatment administration of the cycle but prior to the next cycle administration.
- The onset date is before the treatment administration of the cycle and either:
 - The severity of the event worsened on or after the treatment administration of the cycle.
 - The event became serious on or after the treatment administration of the cycle.

Overall summary of TEAEs will be provided on a per-patient basis for categories of all TEAEs, treatment-related TEAEs, injection procedure-related TEAEs, study drug-related TEAEs, serious TEAEs (STEAEs), deaths, and TEAEs leading to study discontinuation. Each category (except deaths) will be further classified into ocular and nonocular subcategories.

The number and percentage of patients reporting TEAEs will be provided on a per-patient basis by 1) SOC and preferred term; 2) SOC, preferred term and severity in descending order of frequency for each treatment group.

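### By-cycle safety tables compare a 20-week Cycle 3 with 16-week Cycles 1 and 2 as crude percentages, which overstates late-onset events in Cycle 3 at unchanged risk

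*SAP*

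**What the plan says.** SAP section 11.0 gives both the scope and the purpose of the windows: "For all safety by-cycle summary analyses, in order to compare cycles of similar duration, the data included in each cycle will be" as then listed. The list is:

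- "Cycle 1 (16 weeks): data from the 1st injection to the 2nd injection date -1 or upper bound of week 15 visit window" (the second end point applies if there was no 2nd injection);
- "Cycle 2 (16 weeks): data from the 2nd injection to the 3rd injection date -1 or upper bound of week 31 visit window" (likewise, if there was no 3rd injection);
- "Cycle 3 (20 weeks): data from the 3rd injection to upper bound of week 52 visit window";
- a separate extended follow-up row for data after Week 52 in patients who had three injections.

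The lengths follow from the dosing schedule. Protocol section 5.10 states: "Administration of Bimatoprost SR will occur at fixed intervals of 16 weeks, up to a total of 3 administrations". Protocol section 5.6 places these on Day 1, Week 16 and Week 32, and the treatment period is 52 weeks.

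SAP section 11.0 summarizes categorical safety variables by number and percentage of patients. SAP section 11.1 repeats the ocular TEAE analyses by treatment cycle. Within each cycle it also splits ocular TEAEs into those identified within 2 days of administration and those identified later.

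SAP section 11.1 defines a cycle TEAE by onset date: "The onset date is on or after the treatment administration of the cycle but prior to the next cycle administration". An earlier event also qualifies if it worsened or became serious on or after that cycle's administration. No end date is attached to these two criteria, and 11.1 does not refer back to the 11.0 windows.

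**The concern.** At the same underlying risk, the proportion of patients with at least one event over 20 weeks cannot be lower than over 16 weeks. It is higher for any event type that can start in weeks 16 to 20. A crude percentage does not absorb that difference, and printing the window length beside it does not correct it.

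The safety hypothesis in both documents covers single and repeat administration, so a reader will naturally look down the cycle columns for a rise after the third administration. With unequal windows, such a rise in later-onset events could be an artefact. A real rise could equally be dismissed as one.

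**Working it through.** **Window lengths.** From administrations at weeks 0, 16 and 32 and the end of treatment at week 52:

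- Cycle 1: 16 − 0 = 16 weeks
- Cycle 2: 32 − 16 = 16 weeks
- Cycle 3: 52 − 32 = 20 weeks

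This reproduces the lengths printed in SAP 11.0. The ratio is 20/16 = 1.25.

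**Constant hazard.** The documents give no per-cycle event rates, so the 16-week risk p is an assumption and a range is shown. The 20-week risk is 1 − (1 − p)^(20/16).

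| Assumed 16-week risk | 20-week risk | Ratio |
|---|---|---|
| 1% | 1.25% | 1.25 |
| 5% | 6.2% | 1.24 |
| 10% | 12.3% | 1.23 |
| 20% | 24.3% | 1.22 |
| 30% | 36.0% | 1.20 |
| 50% | 58.0% | 1.16 |

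With 200 patients in a group and a 20% risk, this is 200 × 0.20 = 40 against 200 × 0.243 ≈ 49 patients with an event.

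**Events clustered at the injection.** Let a share f of the 16-week cumulative hazard H fall in the first 2 days, with the rest spread evenly and continuing at the same rate. Sixteen weeks is 112 days and 20 weeks is 140 days, so the later part grows by (140 − 2)/(112 − 2) = 138/110. Then H20 = fH + (1 − f)H × 138/110, and the 20-week risk is 1 − exp(−H20). For p = 20%, H = −ln(0.80) = 0.2231.

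| Share f in first 2 days | H20 | Cycle 3 percentage (Cycles 1 and 2: 20.0%) |
|---|---|---|
| 2/112 (constant hazard) | 0.2789 | 24.3% |
| 50% | 0.1116 + 0.1400 = 0.2515 | 22.2% |
| 80% | 0.1785 + 0.0560 = 0.2345 | 20.9% |
| 90% | 0.2008 + 0.0280 = 0.2288 | 20.5% |
| 100% | 0.2231 | 20.0% |

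**The later-than-2-days row alone.** Here the split gives no protection. With f = 50%, the late hazard is 0.1116 over 16 weeks and 0.1400 over 20 weeks, so the row goes from 10.6% to 13.1% (ratio 1.24). With f = 80% it goes from 4.4% to 5.4% (ratio 1.25).

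**Window edges.** The visit-window bounds in SAP 16.1 are redacted, so 20 weeks is nominal. Under constant hazard at a 20% 16-week risk, a cycle cut at 15 weeks would show 18.9%. One running to 21 or 22 weeks would show 25.4% or 26.4%. These are illustrations, not figures from the plan.

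**The case against.** The strongest reply is that this is an open choice and not an error. The SAP asks for similar durations, not equal ones, and prints each length. Week 52 ends the treatment period and coincides with a planned database lock. Capping Cycle 3 there, with a separate follow-up row, already stops it running to Month 20. That stands: a reader who infers that the SAP contradicts itself goes too far.

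A reader might also infer that Cycle 3 percentages will rise by 20 to 25% across the board. The documents do not support that. Protocol section 1.3.3 reports that most adverse events in the earlier study occurred within the first 2 days after administration. For those events the effect is close to zero, and SAP 11.1 already shows them separately. Protocol section 1.3 expects drug release over about 3 to 4 months, so a constant drug-related hazard through weeks 16 to 20 is not established either. Observed Cycle 3 percentages could even fall, because only patients who received the 3rd administration enter that cycle.

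A reader might infer that the safety comparison with timolol is biased. It is not: the control group has the same Cycle 3 window, and no test between cycles appears in the visible text.

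Finally, one could infer that 11.0 and 11.1 produce different counts, because the 11.1 onset rule has no closing date when there is no next administration. That is not established. Section 11.0 claims to govern all by-cycle safety summaries, so it can be read as closing the cycle before 11.1 classifies the event. What stands is that 11.1 does not say so.

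**Conclusion.** The point holds as a comparability weakness in a descriptive table, with a cheap remedy. The comparison between cycles that SAP 11.0 sets out to make is not fair on duration for later-onset events, and the visible plan contains nothing that corrects for it.

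At an assumed 20% risk over 16 weeks, the artefact in the all-event percentage ranges from nil to 4.3 percentage points (20.0% to 24.3%), depending on how strongly events cluster at the injection. It is concentrated in the later-than-2-days row, where the relative excess stays near 24 to 25% in the clustered examples above. These sizes rest on assumed rates and timing, on nominal window lengths, and on risk being the same in every cycle.

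Between-group comparisons within Cycle 3, the overall TEAE tables and all efficacy analyses are untouched. Parts of SAP section 11 are redacted, so an exposure-adjusted summary there cannot be ruled out.

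**What to change.** Keep the planned Cycle 3 table to Week 52. Beside it, for every by-cycle TEAE summary, add one of the following:

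1. a Cycle 3 column cut at 16 weeks after the 3rd administration; or
2. exposure-adjusted rates per patient-time for every cycle.

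The 16-week column is the more robust choice because it equalizes duration whatever the event timing. Rates per patient-time equalize only when the hazard is roughly constant. At a 20% 16-week risk they then give −ln(0.80)/16 = 1.39 per 100 patient-weeks in each cycle. For events confined to the first 2 days, the longer denominator would instead make the Cycle 3 rate about 16/20 = 0.80 of the others. If rates are chosen, they should be read together with the 2-day split.

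In SAP 11.1, state that the cycle TEAE definition, including the worsening and became-serious criteria, uses the start and end dates in 11.0.

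The cost is SAP wording, programming, and one extra column or table, with no new data and no loss of alignment with the Week 52 lock. The 16-week cut does not remove selection. Under Protocol sections 5.6.1 and 5.10, patients with safety concerns may not be re-administered, and implant study eyes on nonstudy IOP-lowering medication receive Sham. A footnote giving the number entering each cycle would make this visible.

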5.6.1 Treatment Regimen/Dosage Adjustments

Patients who have received nonstudy topical IOP-lowering medication (prohibited before Week 52 unless required for safety reasons due to inadequate IOP control and attested to by the investigator) in a Bimatoprost SR study eye will receive Sham administration in that eye on the Bimatoprost SR repeat administration day(s). Patients who have received nonstudy topical IOP-lowering medication in a fellow eye or a Control Group study eye will continue to receive Sham administration in that eye on the administration day(s).

Patients who have received nonstudy IOP-lowering medication in both eyes will not undergo Bimatoprost SR administration or Sham administration in either eye.

Patients who use nonstudy IOP-lowering medication (prohibited before Week 52 unless required for safety reasons due to inadequate IOP control and attested to by the investigator) in only one eye will be followed for the duration of the study. If used in both eyes, patients will be followed at minimum for 12 months after the last administration of Bimatoprost SR or Sham. Patients using nonstudy IOP-lowering medications in both eyes prior to the Week 16 or Week 32 Administration Day will not attend the administration visit(s), nor will they attend the Day 2, Days 4 and 8 (phone call), or 2-week visits (ie, Weeks 2, 18, and 34) following an administration. They would continue the schedule at Week 22 or Week 38, as appropriate for the administration cycle.

Patients who have received nonstudy IOP-lowering medication in both eyes before the time of the Month 14 visit are not required to attend the Month 14 or 18 visits unless the visit is 12 months after their last injection or Sham, at which time the patient may exit early and should complete all Month 20/Exit visit examinations. Patients who have received nonstudy IOP-lowering medication in both eyes by the time of the Month 16 visit are not required to attend the Month 18 visit, unless that visit is 12 months after their last injection or Sham, at which time the patient may exit early and should complete all Month 20/Exit visit examinations.

For patients who have not received nonstudy IOP-lowering medications by the time of study discontinuation or completion, poststudy evaluations regarding the need for IOP-lowering medications should be conducted according to the treating physician's clinical opinion.

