The number and percentage of patients reporting nonocular TEAEs in each treatment group will be tabulated by SOC and preferred term. Also the number and percentage of patients reporting treatment-related (including study drug related or injection procedure related) nonocular TEAEs in each treatment group will be tabulated by SOC and preferred term.

Similar analyses will be done for ocular TEAEs including 1) by PT and severity; 2) treatment-related TEAEs by PT for each treatment group by study eye and fellow eye. In addition, similar analyses will be performed for ocular TEAEs by treatment cycle.

Within each treatment cycle, ocular TEAEs identified (onset or worsened) within 2 days of administration and identified more than 2 days of administration of each cycle will be summarized by each treatment group for study eye and pooled for fellow eye.

Serious TEAEs

Nonocular and ocular STEAEs will be summarized by preferred term and treatment group, respectively.

TEAEs Leading to Study Discontinuation

Nonocular TEAEs and ocular TEAEs leading to premature discontinuation of the study will be summarized by preferred term and treatment, respectively.

Similarly, ocular TEAEs leading to premature discontinuation will also be tabulated by treatment group by treatment cycle.

Ocular TEAEs Leading to Study Drug Discontinuation or Regimen Change

Ocular TEAEs leading to study drug discontinuation will be summarized by preferred term and treatment for the entire study period and also for each cycle. Ocular TEAEs leading to study drug discontinuation or regimen change are defined as the ocular TEAEs with action regarding study drug reported as “Discontinued” or “Regimen Changed” on the eCRF AE form.

Ocular TEAEs Leading to Implant Removal

Ocular TEAEs leading to implant removal will be summarized by preferred term and treatment for the entire study period and also for each cycle.

[REDACTED]

[REDACTED]

[REDACTED]

[REDACTED]

[REDACTED]

[REDACTED]

[REDACTED]

[REDACTED]

[REDACTED]

[REDACTED]

[REDACTED]

[REDACTED]

[REDACTED]

[REDACTED]

[REDACTED]

[REDACTED]

[REDACTED]

[REDACTED]

[REDACTED]

[REDACTED]

[REDACTED]

[REDACTED]

[REDACTED]

[REDACTED]

[REDACTED]

[REDACTED]

[REDACTED]

[REDACTED]

[REDACTED]

[REDACTED]

[REDACTED]

[REDACTED]

[REDACTED]

[REDACTED]

[REDACTED]

[REDACTED]

[REDACTED]

[REDACTED]

[REDACTED]

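### SAP 11.0 assigns late safety data from patients who stop after one or two administrations to none of its four periods, and 11.1 does not say that its cycle rule follows those periods

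*SAP*

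**What the plan says.** SAP 11.0 sets the data that enter every by-cycle safety summary and gives its aim as comparing cycles of similar length. It lists four periods:

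- Cycle 1 runs from the first injection "to the 2nd injection date -1 or upper bound of week 15 visit window (section 16.1") when there is no second injection.
- Cycle 2 runs from the second injection "to the 3rd injection date -1 or upper bound of week 31 visit window (section 16.1") when there is no third.
- Cycle 3 runs from the third injection to the upper bound of the Week 52 window.
- The last is "Extended safety follow up: data after week 52 for patients with 3 injections and extended follow up".

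SAP 11.1 then defines a cycle TEAE by onset: "The onset date is on or after the treatment administration of the cycle but prior to the next cycle administration". An event that began earlier also counts if "The severity of the event worsened on or after the treatment administration of the cycle", or if it became serious in the same time frame.

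The protocol expects some patients to have fewer than three administrations. Under Protocol 5.10 the investigator may withhold a repeat implant if "it would not be in the best interest of the patient to readminister Bimatoprost SR based on previous adverse events or safety concerns". Under Protocol 5.6.1, "Patients who have received nonstudy IOP-lowering medication in both eyes will not undergo Bimatoprost SR administration or Sham administration in either eye". Protocol 8.9 keeps both these patients with medication in both eyes and those who miss a Cycle 2 or 3 administration visit under safety follow-up for 12 months after the last administration.

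SAP 7.0 defines a study completer as a patient with at least one injection who completes the extended safety follow-up visits.

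**The concern.** The four periods do not cover everyone. A patient with no further administration leaves Cycle 1 or Cycle 2 at a window bound and can enter neither Cycle 3 nor extended follow-up, since both require a third injection. The protocol deliberately collects safety data on this patient for most of a year after that point.

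The group is unlikely to be a random subset, because one route into it is a decision not to redose on safety grounds. The time at issue also matters. Protocol 1.3 expects drug release to last about 3 to 4 months but allows about 12 months for more than 75% of the polymer to degrade. The SAP plans by-cycle displays in which such events would be looked for, for example: "Ocular TEAEs leading to implant removal will be summarized by preferred term and treatment for the entire study period and also for each cycle".

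SAP 7.0 does not fit the limit either. A one-injection patient can count there as having completed extended follow-up, while 11.0 gives that patient no extended follow-up period.

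**Working it through.** **Inputs.** Administrations are at Weeks 0, 16 and 32 (Protocol 5.6). The cycle ends are those in SAP 11.0. Minimum follow-up is 12 months, taken as 52 weeks, after the last administration (Protocol 8.9). The window bounds in SAP 16.1 are redacted, so I assume an upper bound 0 to 3 weeks after the nominal visit: Week 15-18 for the first cut and Week 31-34 for the second.

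**The plan's own figures.** 16 - 0 = 16, 32 - 16 = 16 and 52 - 32 = 20 weeks. These match the cycle lengths in SAP 11.0.

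**Unassigned time.** Formula: end of follow-up minus the cut.

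| Administrations | Cut (week) | Follow-up ends (week) | In no period (weeks) | Share of follow-up |
|---|---|---|---|---|
| 1 | 15 to 18 | 0 + 52 = 52 | 52 - 15 = 37 to 52 - 18 = 34 | 37/52 = 71% to 34/52 = 65% |
| 2 | 31 to 34 | 16 + 52 = 68 | 68 - 31 = 37 to 68 - 34 = 34 | 37/68 = 54% to 34/68 = 50% |
| 3 | none | any | 0 | 0% |

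Measured from the last administration, both upper rows describe the same gap: from Week 15-18 (31 - 16 = 15, 34 - 16 = 18) to Week 52. These are minimum figures, because Protocol 8.8 permits exit at 12 months but does not require it.

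**Who is in the gap.** Control patients receive only Sham, so the 11.0 cycles can apply to them only if *injection* includes Sham. SAP 9.1 uses the word in that way. A study eye given Sham in place of a repeat implant (Protocol 5.6.1) therefore stays in the scheme, and the gap concerns patients with no further administration of either kind.

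**11.0 beside 11.1 read alone.** Example onsets:

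| Patient and onset | Period under 11.0 | Cycle under 11.1 alone |
|---|---|---|
| 1 administration, Week 40 | none | Cycle 1 |
| 2 administrations, Week 40 | none | Cycle 2 |
| 3 administrations, Week 60 | extended follow-up | Cycle 3 |

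Where a next administration occurs, the two sections end the cycle at the same point. They part only in a patient's last cycle, where the onset rule has nothing to stop it.

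The worsening branch has no upper bound in any cycle. Take a three-administration patient whose event starts in Cycle 1 and worsens once, at Week 40. Under 11.1 alone it qualifies for Cycle 1 (onset), Cycle 3 (worsening) and also Cycle 2, because Week 40 is after Week 16. If the 11.0 periods govern, Cycle 2 data end the day before the third injection and the Cycle 2 count disappears.

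**The case against.** **The cut is deliberate.** A cycle that ran on for a year in patients who were not redosed would defeat the aim of similar cycle lengths. This stands as a reason to end the cycle. It does not explain why the remaining data go nowhere when a follow-up period already exists for other patients.

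**Nothing is lost.** A reader might infer that late events in this group vanish from the safety analysis, or that the overall comparison with Control is biased. The documents do not support that. The whole-study TEAE tables have no such cut, and events leading to implant removal are tabulated for the whole study as well as by cycle. Protocol 7.3.4 promises both kinds of table, but not that every patient-week falls in a period.

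**11.0 governs 11.1.** A reader might infer that the cycle tables will double-count worsened events, or that a last cycle will run 52 weeks instead of 15-18. Both follow only if 11.1 is read apart from its parent section. 11.0 claims all by-cycle safety summaries and can fairly be taken to cap 11.1, which removes both effects. What stands is that 11.1 states its own start and end rules without referring to those periods. Even on the capped reading, the gap in 11.0 remains.

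**Sham in place of an implant.** One could also argue that eyes switched to Sham need their own display. Given the usage in SAP 9.1 and an all-Sham Control group, a note on the term is enough.

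**Text that cannot be seen.** Parts of 11.0, 11.1 and 16.1 are redacted, and SAP 4.0 places table specifications in a separate document. Later data may be displayed there. The four-item list itself is fully visible, and it leaves these data out.

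**Conclusion.** The point holds as a minor defect in period definitions. Safety data after the Week 15 or Week 31 cut, from patients with no further administration, belong to none of the four periods in SAP 11.0. That is 34-37 weeks per such patient at 12 months of follow-up, or 65-71% of follow-up after one administration and 50-54% after two. The result rests on the assumed 0-3 week window bounds and on reading *injection* to include Sham. The documents do not give the number of such patients, so no trial-level total can be stated.

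The effect is confined to by-cycle and extended-follow-up displays. The missing link between 11.1 and 11.0 is a separate request for clarification; it is a conflict only if 11.0 is not taken to govern.

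**What to change.** 1. In SAP 11.0, extend the follow-up period to all treated patients, from the end of their last cycle window to exit, and show it by number of administrations received. This also brings 11.0 into line with the completer definition in SAP 7.0.
2. In SAP 11.1, state that cycle TEAEs, including events that worsened or became serious, are limited to the 11.0 periods, so that each onset or worsening counts only in the period in which it occurs.
3. Add a note to 11.0 that *injection* includes Sham, consistent with SAP 9.1.

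The cost is SAP wording and table programming; the data are already collected under the protocol. The drawback is a few more table rows.
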